## 6.0 DRUG INFORMATION

### 6.1 Palbociclib (Investigational Drug)

#### 6.1.1 Description

Palbociclib is an inhibitor of CDKs 4 and 6. Cyclin D1 and CDK 4/6 are downstream of signaling pathways, which lead to cellular proliferation. In vitro experiments demonstrated that palbociclib blocks cell cycle progression from G1 into S phase and increases cellular senescence and inhibits tumor growth.

Full prescribing information for palbociclib is available at:

<http://labeling.pfizer.com/ShowLabeling.aspx?id=2191#section-14>

#### 6.1.2 Dosage and Administration

Palbociclib is a 125 mg (100 mg or 75 mg) capsule taken orally once daily for 21 consecutive days followed by 7 days off treatment to comprise a complete cycle of 28 days.

- Palbociclib should be taken with food.
- Patients should be instructed to take their dose of palbociclib at approximately the same time each day.
- If the patient vomits or misses a dose, an additional dose should not be taken. The next prescribed dose should be taken at the usual time.
- Palbociclib capsules should be swallowed whole (do not chew, crush, or open them prior to swallowing).
- Capsules should not be ingested if they are broken, cracked, or otherwise not intact.

#### 6.1.3 Storage and Handling

Palbociclib is supplied in the following strengths

Palbociclib capsules	
Package configuration	Capsule strength (mg)
Bottles of 21 capsules	125
Bottles of 21 capsules	100
Bottles of 21 capsules	75

Store at 20 °C to 25 °C (68 °F to 77 °F); excursions between 15 °C to 30 °C (59 °F to 86 °F) permitted

#### 6.1.4 Drug Accountability

The investigator or designee is responsible for keeping accurate records of the clinical supplies received from the company sponsor or designee, the amount dispensed to the subjects and the amount remaining at the conclusion of the trial. An accurate and current accounting of the dispensing and return of investigational study drug for each subject will be maintained on an ongoing basis by a member

of the study site staff. The amount of study drug dispensed and returned by the subject will be recorded in the Investigational Drug Accountability Record.

#### 6.1.5 Return and Retention of Study Drug

Upon completion or termination of the study, all unused and/or partially used investigational product will be destroyed at the site per institutional policy (eg, UNC IDS drug destruction policy). It is the Investigator's responsibility to arrange for disposal of all empty containers, provided that, procedures for proper disposal have been established according to applicable federal, state, local and institutional guidelines and procedures, and provided that appropriate records of disposal are kept.

#### 6.1.6 Adverse Events Associated with Palbociclib

The AEs provided below are common toxicities associated with palbociclib per March 2017 IB. For additional details, please consult the current IB.

Pooled Adverse Drug Reactions Reported for Patients who received Palbociclib in Randomized Clinical Studies A5481003, A5481008, and A5481023 (N = 872)

System Organ Class Preferred term (PT) a	Frequency	All Grades n (%)	Grade 3 n (%)	Grade 4 n (%)
Infections & Infestations				
Infections	Very common	501 (57.5)	40 (4.6)	8 (0.9)
Blood and lymphatic system disorders				
Neutropenia	Very common	712 (81.7)	497 (57.0)	93 (10.7)
Leukopenia	Very common	420 (48.2)	249 (28.6)	7 (0.8)
Anemia	Very common	247 (28.3)	41 (4.7)	2 (0.2)
Thrombocytopenia	Very common	182 (20.9)	14 (1.6)	4 (0.5)
Febrile neutropenia	uncommon	11 (1.3)	10 (1.1)	1 (0.1)
Eye disorders				
Vision blurred	Common	44 (5.0)	1 (0.1)	0 (0.0)
Lacrimation increased	Common	56 (6.4)	0 (0.0)	0 (0.0)
Dry eye	Common	32 (3.7)	0 (0.0)	0 (0.0)
Metabolism and nutrition disorders				
Decreased appetite	Very common	147 (16.9)	8 (0.9)	0 (0.0)
Nervous system disorders				
Dysgeusia	Common	78 (8.9)	0 (0.0)	0 (0.0)
Respiratory, thoracic and mediastinal disorders				
Epistaxis	Common	77 (8.8)	0 (0.0)	0 (0.0)
Gastrointestinal disorders				
Stomatitis	Very common	260 (29.8)	7 (0.8)	0 (0.0)
Nausea	Very common	311 (35.7)	5 (0.6)	0 (0.0)
Diarrhea	Very common	230 (26.4)	9 (1.0)	0 (0.0)
Vomiting	Very common	158 (18.1)	5 (0.6)	0 (0.0)
Skin and subcutaneous tissue disorders				
Rash	Very common	151 (17.3)	7 (0.8)	0 (0.0)

Alopecia	Very common	232 (26.6)	0 (0.0)	0 (0.0)
Dry skin	Common	88 (10.1)	0 (0.0)	0 (0.0)
General disorders and administration site conditions				
Fatigue	Very common	359 (41.2)	20 (2.3)	2 (0.2)
Asthenia	Common	115 (13.2)	13 (1.5)	1 (0.1)
Pyrexia	Common	113 (13.0)	1 (0.1)	0 (0.0)
Investigations				
AST increased	Very common	88 (10.1)	23 (2.6)	0 (0.0)
ALT increased	common	84 (9.6)	16 (1.8)	1 (0.1)

N/n = number of patients

Frequencies are defined as: very common ( $\geq 1/10$ ); common ( $\geq 1/100$ ); uncommon ( $\geq 1/1000$  to  $< 1/100$ ); rare ( $\geq 1/10,000$  to  $N1/1000$ )

a. Preferred terms according to MedDRA 17.1

Palbociclib use is associated with increased of neutropenia and embryo-fetal toxicity. Patients need to inform their physician promptly of any episodes of fever.

**Embryo-fetal toxicity:** Palbociclib can cause harm to the fetus. Patients should be advised of potential risk to the fetus and WOCBP must use adequate contraception during treatment and for at least 30 days after the last dose of palbociclib.

## 6.2 Cetuximab (Erbitux®) (Commercial Drug)

### 6.2.1 Description

Cetuximab is a recombinant, human/mouse chimeric monoclonal antibody that binds specifically to the extracellular domain of the human EGFR. Cetuximab is composed of the Fv regions of a murine anti-EGFR antibody with human IgG1 heavy and kappa light chain constant regions and has an approximate molecular weight of 152 kilodaltons.

Cetuximab is supplied at a concentration of 2 mg/mL as a 100mg/50mL, single use vial or as a 200 mg/100mL, single-use vial as a sterile, injectable liquid containing no preservatives.

Full prescribing information for cetuximab is available at:  
[http://uspl.lilly.com/erbitux/erbitux.html#Section\\_2.4](http://uspl.lilly.com/erbitux/erbitux.html#Section_2.4)

### Dosage and Administration:

Cetuximab will be administered on a weekly basis in this trial per the standard dosing regimen described below.

- The recommended initial dose is 400 mg/m^2 administered as a 120-minute IV infusion (maximum infusion rate 10 mg/min)
- The recommended subsequent weekly dose (all other infusions) is 250 mg/m^2 infused over 60 minutes (maximum infusion rate 10 mg/min) until disease progression or unacceptable toxicity

**Administer through a low protein binding 0.22-micrometer in-line filter.**

**Storage and Stability:**

Store vials under refrigeration at 2 °C to 8 °C (36 °F to 46 °F). **Do not freeze.**

Preparations of cetuximab infusion are chemically and physically stable for up to 12 hours at 2 °C to 8 °C (36 °C to 46 °F) and up to 8 hours at controlled room temperature (20 °C to 25 °C; 68 °F to 77 °F)

**Handling and Disposal:** Local requirements for disposal of hazardous drugs should be followed at each participating clinical site.

Please see UNC policy on hazardous drugs:

<http://news.unchealthcare.org/empnews/att/2011/nov/admin0188/>.

#### **6.2.2 Adverse Events Associated With Cetuximab**

**Infusion reactions:** serious reactions, requiring medical intervention and immediate and permanent discontinuation of cetuximab included rapid onset of airway obstruction, hypotension, shock, loss of consciousness, myocardial infarction, and/or cardiac arrest. Approximately 90% of severe infusion reactions occurred with the first infusion despite premedication with antihistamines. See section 5.3.3 for management guidelines for infusion-related reactions.

**Cardiopulmonary arrest:** and/or sudden death occurred in 4 (2%) of 208 patients treated with radiation therapy and cetuximab.

**Pulmonary toxicity:** Interstitial lung disease, including 1 fatality, occurred in 4 of 1570 (<0.5%) patients receiving cetuximab in patients with CRC and head and neck cancer.

**Dermatologic toxicity:** including acneiform rash, skin drying and fissuring, paronychial inflammation, infectious sequelae (eg, aureus sepsis, abscess formation, cellulitis, blepharitis, conjunctivitis, etc.). See sections 5.3.2 for dose modification information. See sections 5.4.1 and Appendix 12.1 for skin toxicity prophylaxis and toxicity management guidelines.

Hypomagnesemia and electrolyte abnormalities: reported incidence in 55% of 365 patients receiving cetuximab for CRC and head and neck cancer, with 6-17% of patients experiencing grade 3 or grade 4 events.

Increased tumor progression, increased mortality or lack of benefit in patients with Ras-Mutant mCRC: Cetuximab is not indicated for use in patients with Ras-mutations of either K-ras, N-ras.

EGFR expression and response: in CRC patients response rate to cetuximab did not correlate with either the percentage of positive cells or the intensity of EGFR expression.

Patient Counseling Information:

Advise patients:

- To report signs and symptoms of infusion reactions such as fever, chills, or breathing problems
- Of the potential risks of using cetuximab during pregnancy or nursing and the need to use adequate contraception in both males and females during and for 6 months following the last dose of cetuximab
- That nursing is not recommended during, and for 2 months following the last dose of cetuximab
- To limit sun exposure (use sunscreen, wear hats) while receiving and for 2 months following the last dose of cetuximab

For additional details, please refer to the cetuximab package insert.

## 7.0 EVALUATIONS AND ASSESSMENTS

### 7.1 Clinical Assessments

Clinical assessments will be performed as outlined in the Time and Events Table in Section 7.4.

#### 7.1.1 Concomitant Medications

All concomitant medication and concurrent therapies will be documented at Baseline/Screening and throughout the study as summarized in the Time and Events Table in Section 7.4. Dose, route, unit frequency of administration, and indication for administration and dates of medication will be captured.

#### 7.1.2 Demographics

Demographic information (date of birth, gender, race) will be recorded at Screening.

### **7.1.3 Medical History**

Relevant medical history, including history of current disease, other pertinent respiratory history (e.g., tobacco use), and information regarding underlying diseases will be recorded at Screening and a focused medical history on symptoms/toxicity will be performed thereafter.

### **7.1.4 Physical Examination**

A complete physical examination including height (at screening only), weight, performance status per Eastern Cooperative Oncology Group (ECOG ) criteria (provided in Appendix 12.3) and **vital signs** (i.e., temperature, heart rate, blood pressure) will be performed by either the investigator or a sub-investigator who is a physician at Screening and on day 1 of the first and second treatment cycle. An abbreviated physical exam may be performed at all other visits and should include vital signs and ECOG performance status.

New abnormal physical exam findings must be documented and will be followed by a physician or other qualified staff at the next scheduled visit.

### **7.1.5 Adverse Events**

Events should be assessed per NCI-CTCAE criteria 4.0.3. Information regarding occurrence of adverse events will be captured throughout the study. Duration (start and stop dates), severity/grade, outcome, treatment and relation to study drug will be recorded in the case report form (CRF).

### **7.1.6 Electrocardiogram**

An electrocardiogram should be performed during the screening period (ie, within 4 weeks of instituting study treatment) to ensure that the subject meets eligibility for enrollment.

### **7.1.7 Disease Assessment (Tumor Measurement)**

CRC disease will be assessed by a contrasted computed tomography scan (CT) of the chest, and a contrasted CT or contrasted MRI of the abdomen and pelvis.

Baseline disease assessment should be obtained within 4 weeks of initiating study treatment, and then conducted every 8 weeks (+/- 7 days) thereafter.

## **7.2 Clinical Laboratory Assessments**

### **7.2.1 Hematology**

Blood will be obtained during the study as outlined in section 7.4 and sent to the clinical site hematology lab for assessment of complete blood count (CBC): (hemoglobin, hematocrit, red blood cell count, white blood cell count, white blood cell differential, and platelet count)

Perform a CBC at screening, on Days 1 and 15 during the first two treatment cycles of combination treatment, on D1 of subsequent cycles (cycle 3 and beyond including the end of treatment visit), and as clinically indicated in subsequent treatment cycles.

Please refer to section 5.3.1 for guidance on how to manage palbociclib-related hematologic toxicity.

#### **7.2.2 Blood Chemistry Profile**

Blood will be obtained and sent to the clinical site chemistry lab for determination of a **Complete Metabolic Panel (CMP)**: (Blood urea nitrogen creatinine, sodium, potassium, chloride, bicarbonate, glucose, calcium, albumin, total protein, total bilirubin, alanine aminotransferase (ALT/SGPT), aspartate aminotransferase (AST/SGOT), and alkaline phosphatase) + **Magnesium**

**Magnesium and Potassium** should be assessed weekly prior to each cetuximab infusion as denoted in the Time and Events table in section 7.4.

Note: On days when CMP is scheduled include Magnesium as part of serum chemistry panel.

After the subject discontinues cetuximab, they must have magnesium and potassium monitored at a minimum as described in Time and Events Table in section 7.4, but with additional lab visits and repletion as clinically indicated per institutional standard.

#### **7.2.3 Other Relevant Tests**

#### **7.2.4 Pregnancy Test**

A urine or serum pregnancy test will be obtained from WOCBP prior to their participation in the study.

This pregnancy test should be obtained within 72 hours of initiating study combination treatment.

#### **7.2.5 Carcinoembryonic antigen (CEA)**

Obtain CEA on D1 of each treatment cycle starting on day 1 of cycle 1, and at the end of treatment visit.

#### **7.2.6 Alpha-gal Test**

In Southeast only, test for galactose-alpha-1,3-galactose IgE must be performed and must be negative to be eligible for this study.

### 7.3 Correlative Studies

We will collect peripheral blood for plasma and serum including two 10-ml tubes of blood for plasma for circulating tumor DNA (such as Na EDTA or Streck tubes) and one 10-ml tube of serum for circulating thymidine kinase activity assay. A limited number of peripheral blood aliquots will be used to collect PMBCs (peripheral mononuclear blood cells) from various time points. These blood samples will be split into cellular and plasma fractions to allow analysis of PMBCs and soluble factors in each sample. Please see the study lab manual for complete details on sample handling procedures.

Additionally, we will plan to test archival tissue and optional on-treatment biopsies for next generation DNA and RNA sequencing. The DNA testing will detect somatic mutations, and specific analysis of germline mutations is not planned. The optional biopsies would be for research purposes and would require consent for these procedures. If insufficient archival tissue is available, the subject can still participate in the clinical trial.

#### 7.4 Time and Events Table

Assessments	Pre-study 	Study Treatment (each cycle is 28-days) 										End Of Treatment 	Day 56 (+/-7 days) Follow up	Long Term Follow up	
		C1 D1	C1 D8	C1 D15	C1 D22	C2 D1	C2 D8	C2 D15	C2 D22	C3-N D1	C3-N D8	C3-N D15	C3-N D22		
Informed Consent	X														
History 	X	X	X	X	X	X	X	X	X	X	X	X	X	X	X
Physical exam	X	X	X	X	X	X	X	X	X	X	X	X	X	X	X
ECOG Performance Status	X	X	X	X	X	X	X	X	X	X	X	X	X	X	X
Electrocardiogram	X														
Tumor measurement 	X														
Pregnancy test	X														
Alpha-gal test 	X														
Hematology	X	X	X	X	X	X	X	X	X	X	X	X	X	X	X
Magnesium & Potassium		X	X	X	X	X	X	X	X	X	X	X	X	X 	X
Complete Metabolic Panel + Mg	X	X	X	X	X	X	X	X	X	X	X	X	X	X	X
CEA	X	X	X	X	X	X	X	X	X	X	X	X	X	X	X
Toxicity Assessment 	X	X	X	X	X	X	X	X	X	X	X	X	X	X	X
Concomitant Meds	X	X	X	X	X	X	X	X	X	X	X	X	X	X	X
Palbociclib															
Patient diary	X														
Cetuximab 400 mg/m 	X														
Cetuximab 250 mg/m  (IV weekly)		X	X	X	X	X	X	X	X	X	X	X	X	X	X
Request archival	X														
Blood sample for correlatives 	X														
Tumor biopsy  (Optional; goal n=5 for each cohort)															
Survival analysis 															X

### Footnotes to Time and Events Table

1. Screening assessments:
  - a. Radiological/electrocardiogram/disease assessments and physical exam may be performed within 4 weeks prior to day 1 of treatment.
  - b. Other evaluations except for pregnancy test must be performed within 2 weeks prior to Cycle 1 Day 1 (C1D1) of treatment.
  - c. Serum or urine  $\beta$ -HCG must be performed **within 72 hours prior** to first dose of study medication for women of child-bearing potential.
  - d. Screening labs performed within 72 hours prior to Cycle 1 Day 1 (C1/D1) do not need to be repeated on C1D1
2. A window of  $+$ / $-$  3 days applies to all study visits unless otherwise specified. The optional on-treatment biopsy scheduled for Cycle 1 Day 22 has a window of  $+$ / $-$  7 days.
3. The end of treatment visit should only occur when patients permanently stop study treatment and should be performed within 30 days ( $+$ / $-$  7 days) after the last dose of study medication. Patients who have an ongoing  $\geq$ grade 2 or serious AE (SAE) at this visit will continue to be followed until the event is resolved or deemed irreversible by the investigator. See section 7.7.3 for long-term follow up plan for this study.
4. Baseline disease assessment should be obtained within 4 weeks of starting study treatment, and then conducted every 8 weeks thereafter ( $+$ / $-$  7 days).
5. Alpha-gal must be negative for any subjects enrolled in Southeastern U.S. sites (See Appendix 12.5). Testing to be performed within 6 months of Day 1 treatment.
6. After a subject discontinues cetuximab, their magnesium and potassium must be monitored for an additional 8 weeks, at a minimum as described in the time and events table, but with additional lab visits and repletion as clinically indicated per institutional standard.
7. Correlative blood draws should occur on day 1 and day 22 of cycles 1 and 2 and then with subsequent even cycles (cycle 4, 6, 8, etc).
8. The Long-term follow up visit will occur every 90 days ( $+$ / $-$  15 days).

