#### 1.4 Palbociclib

The cyclin D-cyclin-dependent kinase (CDK) 4/6-inhibitor or CDK4 (INK)-retinoblastoma (Rb) pathway regulates cellular proliferation by controlling the G1 (pre-DNA synthesis) to S (DNA synthesis) cell cycle checkpoint [17]. This pathway is frequently dysregulated in cancer and aberrant signaling via this checkpoint contributes to cell cycle progression and continued growth.

Palbociclib is a highly selective reversible oral inhibitor of CDK 4 and 6 that is being studied for use in the treatment of cancer [18]. Palbociclib inhibits purified CDK4-catalyzed phosphorylation of the retinoblastoma (Rb) protein with an IC50 of less than 20 nM and also tumor growth of several types of human xenograft tumors (SF-295, MDA-MB-435, Colo-205, and others), grown in severely immunocompromised mice. Estimated steady-state plasma concentrations of 1000 ng/mL resulted in 80% to 90% inhibition of phospho-Rb formation and 50% reduction in tumor growth. Reduction in phospho-Rb was rapidly reversible as plasma palbociclib concentrations declined.

Palbociclib has been approved for the treatment of hormone receptor (HR-positive), human epidermal growth factor receptor 2 (HER)-negative advanced or metastatic breast cancer in combination with an aromatase inhibitor as initial endocrine based therapy in postmenopausal women; or with fulvestrant in women with disease progression following endocrine therapy (Palbociclib USPI). The recommended dosing regimen is 125 mg administered once daily for 21 consecutive days of a 28-day cycle. Palbociclib in combination with letrozole in postmenopausal women (PALOMA-1 and PALOMA-2) [19, 20], or in combination with fulvestrant in women after progression on endocrine therapy (PALOMA-3) [21] significantly improved PFS and improved clinical benefit response rates. Neutropenia was the most commonly reported any grade and grade  $\geq$  3 adverse event (AE) in these trials (66% of patients in PALOMA-2 and PALOMA-3 had  $\geq$  grade 3 neutropenia; median duration 7 days); and was generally manageable with palbociclib dose delays, interruptions or reductions, without the need for growth factor support and without compromising efficacy [17]. The neutropenia was infrequently associated with febrile events (<2%).

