## 1.6 Correlative Studies

Identifying mechanisms of resistance to targeted therapies, including anti-EGFR therapies, is critical to identifying superior combinations of therapies for the future. Resistance to anti-EGFR therapies is accompanied by increases in circulating tumor DNA harboring KRAS mutations, reflecting expansion of KRAS mutated subclones. We will collect peripheral blood samples serially to facilitate analyses such as mutation analysis and quantitation of circulating free tumor DNA. Additionally, we will collect serum samples for analysis of

circulating thymidine kinase activity, which is a reflection of cell proliferation and has been shown to be a pharmacodynamic biomarker in other trials using CDK4/6 inhibitors. We will also collect archival tissue to have available to assess Consensus Molecular Subtypes by mRNA expression analysis, as these subtypes are associated with differential underlying biology and prognosis and may explain heterogeneity of responses of metastatic CRC to various therapies. We will also include an optional on-treatment biopsy to identify potential biomarkers for anti-EGFR antibodies, which could include integrated genomic analysis with multiplex next generation DNA and RNA sequencing and immunohistochemistry for known pharmacodynamic biomarkers of cell proliferation.

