## 5.2 Treatment Dosage and Administration

REGIMEN DESCRIPTION					
Agent	Premedication; Precautions	Dose	Route	Schedule	Cycle Length
Palbociclib	Take palbociclib with food	125mg	oral	Once daily on Days 1-21, then 7 days off	
Cetuximab 	Pretreatment for infusion-related reactions per local standard of care   e.g., 50 mg diphenhydramine, H2 blocker (ranitidine or famotidine) and dexamethasone (8-20 mg)  See section 5.3.2 for guidance on infusion-related reactions	Loading dose: 400 mg/m   Subsequent doses 250 mg/m 	IV, administered over 2 hours  IV, administered over 1 hour (± 15 minutes)	Once weekly, start with loading dose D1 of wk 1 then subsequent doses given D1 of wk 2 and beyond	4 weeks (28 days)

1. In general, a histamine receptor antagonist prior to cetuximab infusion is recommended to prevent hypersensitivity reactions. Corticosteroid premedication may also be given per local guidelines. If hypersensitivity ruled out after the first infusion, premedication(s) may be omitted if permitted per local guidelines.
2. In Southeast only, test for galactose-alpha-1,3-galactose IgE must be performed and must be negative to be eligible for cetuximab therapy.

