## 7.6 Treatment Assessments

Study visits should be performed with +/-3 days of the scheduled assessment unless otherwise specified.

### 7.6.1 D1 of Cycle 1

1. Focused medical history and complete physical examination
2. ECOG Performance status
3. Toxicity Evaluation
4. Concomitant medications
5. Patient diary
6. Laboratory evaluations (do not repeat if performed within last 72 hrs)
  - Hematology
  - Complete Metabolic Panel (CMP) + Magnesium
  - CEA
  - Blood sample for correlates
7. Administer Study Medications (See section 5.2 for details on treatment dosage and administration)

### 7.6.2 D8 of Cycle 1

1. Toxicity Evaluation
2. Concomitant medications
3. Laboratory evaluations)
  - Magnesium (Mg) and potassium
4. Administer Study Medications (See section 5.2 for details on treatment dosage and administration)

### 7.6.3 D15 of Cycle 1

1. Focused medical history and physical examination

2. ECOG Performance status
3. Toxicity Evaluation
4. Concomitant medications
5. Laboratory evaluations
  - Hematology
  - Complete Metabolic Panel (CMP) + Magnesium
6. Administer Study Medications (See section 5.2 for details on treatment dosage and administration)

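### Day 22 is the first palbociclib-free day and about half of each Day 22 sampling window lies in the off-week, which can blur the CDK4/6 pharmacodynamic markers

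*Combined protocol and SAP*

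**What the plan says.** Palbociclib is given "Once daily on Days 1-21, then 7 days off" (section 5.2). Section 6.1.2 agrees: "once daily for 21 consecutive days followed by 7 days off treatment to comprise a complete cycle of 28 days".

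Sampling is set in the footnotes to the Time and Events Table (section 7.4). Footnote 2 reads "The optional on-treatment biopsy scheduled for Cycle 1 Day 22 has a window of" ±7 days. Footnote 7 reads "Correlative blood draws should occur on day 1 and day 22 of cycles 1 and 2", and then in even-numbered cycles. No separate window is given for the blood draws, so the general rule applies: "Study visits should be performed with +/-3 days of the scheduled assessment unless otherwise specified" (section 7.6). Sections 7.6.5 and 7.6.9 list the Day 1 correlative blood ahead of study drug administration.

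On purpose, section 1.6 collects serum for "circulating thymidine kinase activity, which is a reflection of cell proliferation" and says that it "has been shown to be a pharmacodynamic biomarker in other trials using CDK4/6 inhibitors". It presents the biopsy as a search for markers relevant to anti-EGFR antibodies, with proliferation staining as one possible use. Sections 1.6 and 7.3 also plan circulating tumour DNA, and DNA and RNA sequencing of tissue. Section 9.3 plans exploratory logistic and Cox models of disease control, response, PFS and OS on tumour mutations and pharmacodynamic markers, if numbers permit. On the effect itself, section 1.4 says "Reduction in phospho-Rb was rapidly reversible as plasma palbociclib concentrations declined".

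**The concern.** A pharmacodynamic marker of CDK4/6 inhibition depends on how recently the inhibitor was taken. As written, the sampling windows straddle the switch from daily dosing to the week off, and nothing in the supplied text ties a sample to the last palbociclib dose. Two patients with the same biology could be sampled on Day 20 and Day 25 and enter the same section 9.3 model as equivalent observations.

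At stake is the interpretability of the thymidine kinase series and of any proliferation staining. Variation in time off drug adds noise to the marker, and would bias the association if late sampling were related to a patient's course, for example through delayed visits. The table's goal is only 5 biopsies per cohort, so there is little room to sort this out afterwards.

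**Working it through.** The documents state no on-drug or off-drug share, so there is no figure to reproduce. The check is a count of calendar days, assuming uninterrupted dosing with the last dose on Day 21.

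**Inputs.** On drug: Days 1-21. Off drug: Days 22-28 (sections 5.2, 6.1.2; 21 + 7 = 28, which is consistent). Biopsy: Day 22 ±7 (footnote 2). Blood: Day 22 ±3 (footnote 7 and section 7.6).

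**Biopsy window.** 22 − 7 = 15 to 22 + 7 = 29, which is 15 days.
- On drug, Days 15-21: 7 days.
- Off-week, Days 22-28: 7 days, 7/15 = 47%.
- Day 29 is Cycle 2 Day 1. If sampled before that day's dose it is also off drug: 8/15 = 53%.
- Longest time since last dose: 29 − 21 = about 8 days.

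**Day 22 blood window.** 22 − 3 = 19 to 22 + 3 = 25, which is 7 days.
- On drug, Days 19-21: 3 days.
- Off-week, Days 22-25: 4 days, 4/7 = 57%.
- Longest time since last dose: 25 − 21 = about 4 days.

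**Nominal days.** Day 22 is 22 − 21 = 1 day after the last dose, the usual interval between daily doses. Day 1 of a later cycle, drawn before dosing as listed, is Day 29 of the cycle before: about 8 days after the last dose. No nominal on-study draw therefore falls within Days 2-21.

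**Sensitivity of drug level only.** The documents give no half-life. Assuming 12 to 48 hours, the level relative to the usual 24-hour pre-dose level is 0.5^(hours after Day 22 / half-life):

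| Day | Hours after Day 22 | 12 h half-life | 48 h half-life |
|---|---|---|---|
| 22 | 0 | 100% | 100% |
| 25 | 72 | 0.5^6 = 2% | 0.5^1.5 = 35% |
| 28 | 144 | 0.5^12 = under 0.1% | 0.5^3 = 12.5% |

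This shows where in the window exposure would fall away. It says nothing about how fast a marker recovers.

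**After the change.** A Day 15 ±3 draw covers Days 12-18, all on drug. A draw on Days 19-22, or a biopsy on Days 15-22, is at most about 1 day from the last dose.

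**The case against.** The strongest reply is that most of these samples do not have CDK4/6 inhibition as their stated target. The biopsy is aimed at anti-EGFR markers. Two of the three tubes named in section 7.3 are plasma for circulating tumour DNA, which section 1.6 links to resistant subclones. Cetuximab is infused on Day 22, so calling the biopsy on-treatment is correct for that drug. This stands, and it confines the point to serum thymidine kinase and to proliferation staining, if done.

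Second, a reader might infer that a Day 22 sample is taken after the effect has reversed. The documents do not support that. Nominal Day 22 is about one dosing interval after the last capsule, comparable with a pre-dose sample on a treatment day. The reversibility statement in section 1.4 follows an account of xenografts in mice and concerns phospho-Rb, not thymidine kinase, and no recovery time is given. Only the later part of each window is exposed.

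Third, a reader might infer that the windows lie mainly in the off-week, or that no draw falls on a dosing day. The biopsy split is 7 days on, 7 off and 1 at the next Day 1. Day 1 of a later cycle is a dosing day; the valid point is that the draw is listed before the dose. Nor can one say how many of the 5 biopsies would be off drug, because section 7.6.4 places the biopsy at the Day 22 visit and an even spread over the window is not supported.

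Finally, the exploratory objectives are redacted, the laboratory manual is not supplied, and a patient diary is kept, so dose dates may be recoverable. That is fair. Even so, no supplied section links the diary to the samples or uses time since dose in the analysis.

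**Conclusion.** The point holds as a minor design improvement. About half of each window (biopsy 7/15, or 8/15 with a pre-dose Day 29; Day 22 blood 4/7) lies off palbociclib, late samples can be about 4 days (blood) or 8 days (biopsy) from the last dose, and the section 9.3 text would pool them with on-drug samples.

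The size of the effect on any marker cannot be computed from the documents. It would be too strong to conclude that associations with outcome would be reversed or that the biopsy set would lose its value: mutation sequencing and circulating tumour DNA are not shown to depend on palbociclib timing. The primary endpoint and both Simon designs are untouched.

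The conclusion assumes uninterrupted dosing to Day 21 and Day 1 draws in the listed order. Because section 5.3.1 allows palbociclib to be withheld, actual time since dose may vary more than the calendar shows.

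**What to change.** Change sampling only and leave dosing as it is.

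1. Footnote 7: take the thymidine kinase serum at the existing Day 15 visit, where blood is already drawn, or restrict that draw to Days 19-22. Keep the Day 22 draws for circulating tumour DNA.
2. Footnote 2: when proliferation markers are to be assayed, end the biopsy window at Day 22 (Days 15-22).
3. Record time since last palbociclib dose with every sample.
4. Section 9.3: use that time in the pharmacodynamic models, and analyse samples taken later in the off-week separately.

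The cost is two footnote edits, one data field, a narrower window for an optional biopsy, and less comparability with samples already taken under the current schedule. If the window cannot be narrowed, items 3 and 4 alone still recover part of the benefit.
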